For Sample 1, Hypothesis 1: We will investigate the association between Prog and self-reported craving with a linear regression model. A multiple linear regression model will be used to see if the relationship changes with consideration of other baseline measures (including cigarettes/day). Similar analyses will be performed comparing the change in Prog with the change in self-reported craving from Day 0 to Day 7. Hypothesis 2a: For this analysis, we will investigate the association between Prog and self-reported craving after overnight abstinence with a linear regression model. A multiple linear regression model will be used to see if the relationship changes with consideration of other baseline measures, such as cigarettes/day and FTND score. Hypothesis 2b: We will investigate the association between Prog and heart rate outcome at five minutes post nicotine nasal spray using a linear regression model. A multiple linear regression model will be used to see if the relationship changes with consideration of other baseline measures (including cigarettes/day). We will also explore how Prog impacts the nicotine exposure outcomes over time using repeated measures models to account for within-subject correlation. For Hypothesis 1, 2a, and 2b, similar analyses will be performed for the secondary outcomes and the independent variables (Allo, E2/P).

Table 3. Data & Statistical Analysis Comparison of the Two Study Samples

	Sample 1 Pregnant Women (n=84)	Sample 2 Oral Contraceptive (OC) Users (n=52)
Independent Variable Collection	Both samples complete identical procedures : 
 • Serum progesterone, allopregnanolone, and estradiol (Day 0, Day 7) 	
Dependent Variable Collection	Both samples complete identical procedures : 
 • Aim 1 - Smoking-related symptomatology collected via EMA (Day 1-7) • Aim 2 - Smoking-related symptomatology collected during ad libitum smoking (Day 0, Day 7) and after overnight abstinence (Day 8). Nicotine response measures collected during three-hour lab session (Day 8). 	
Statistical Analysis	
 • Aim 1 - Linear regression • Aim 2 - Linear regression 	
 • Aim 1 - Repeated measures model • Aim 2 - Repeated measures model
	Comparison of Clinical Models - Linear regression with propensity scores (baseline characteristics) and clinical model indicator variable	

A multiple linear regression model will be used to see if the relationship changes with consideration of other baseline measures, such as cigarettes/day and FTND score. Hypothesis 2b: We will investigate the association between Prog and heart rate outcome at five minutes post nicotine nasal spray using a linear regression model. A multiple linear regression model will be used to see if the relationship changes with consideration of other baseline measures (including cigarettes/day). We will also explore how Prog impacts the nicotine exposure outcomes over time using repeated measures models to account for within-subject correlation. For Hypothesis 1, 2a, and 2b, similar analyses will be performed for the secondary outcomes and the independent variables (Allo, E2/P).

For Sample 2, Hypothesis 1: We will analyze self-reported craving (primary) using a repeated measures model. A random intercept will be included to model within subject correlation. OC level ("low" or "high" dose), testing period (first or second) and sequence will be included in the model as fixed effects. Hypothesis 2a: For this analysis, we will use self-reported craving, urges to smoke and stress collected after overnight abstinence. As in Hypothesis 1, repeated measures models will be used to compare the self-reported craving outcome between hormonal OC level groups. Hypothesis 2b: Again, repeated measures models will be used to compare the heart rate outcome between hormonal OC level groups at the first time point after baseline. We will also explore the heart rate outcome over time by using a covariance structure to model repeated measures on subjects at each visit. For Hypothesis 1, 2a, and 2b, similar analyses will be performed for the secondary outcomes and the independent variables (Allo, E2/P).

To compare the two study samples we will use all data from Sample 1 and data from the first testing period only for Sample 2. To compare outcomes between Sample 1 and Sample 2, we will use a propensity score ⁶⁵ to balance the baseline covariates in the two groups. A linear regression model will be used to investigate the association between Prog and the self-reported craving outcome. An indicator variable for group, the propensity score quintile, Prog and a group by Prog level interaction will be included in the model as independent variables. Similar analyses will be conducted for the secondary outcomes and the independent variables (Allo, E2/P)

Strengths & Limitations. This study has several strengths. First, and foremost, is the use of two unique clinical models to investigate the effects of sex hormones on smoking-related symptomatology. This study will be among the first to utilize this type of study design. Further, the cross-over study design used with Sample 2 will limit confounding given that each participant is compared to herself. An additional strength is the detailed measurement of smoking status, sex hormones, smoking-related symptomatology, withdrawal symptoms and nicotine response. Finally, the study team has extensive experience and expertise, which provides unique qualifications to pursue this research project. Three limitations are worth noting. First, we do not have a sample of males for comparison. The relevance for needing this comparison group may be of lesser importance considering that female sex hormones are the main interest. Second, due to the experimental design and the use of a convenience sample, we will have limited generalizability. Finally, given that we will be completing the nicotine exposure session among pregnant smokers who report current daily smoking, it is possible that we will have a biased sample. However, the ethical concerns of administering nicotine to a pregnant woman who has quit smoking, makes this limitation unavoidable. Therefore, to investigate the possibility of a biased sample difference in associations between sex hormones (Prog, Allo, E2/P) with smoking-related symptomatology and nicotine response we will also look at a subgroup of women who reduced their smoking during pregnancy (>50% reduction) versus those who maintained their self-reported pre-pregnancy smoking rate. Specifically, we will include an indicator variable for smoking reduction and the interaction between this indicator and sex

hormone in the models. Despite these limitations, this study provides a unique opportunity and excellent conditions for testing our overall study objective.

Study Team. Our research team has unique breadth and depth of expertise in the following areas: effects of ovarian hormones (menstrual phase, hormone replacement therapy) on smoking cessation in women ([name], PI); nicotine dependence, smoking cessation, and tobacco toxin exposure ([name], Co-I); cortisol measurement of stress ([name], Co-I) and mental health and pregnancy ([name], Co-I). We will also be utilizing

Table 4. Study Timeline

	Year 1			Year 2			Year 3			Year 4			Year 5		
Training Staff & Study Preparation	X	X	X												
Participant Recruitment			X	X	X	X	X	X	X	X	X	X	X	X	X
Participant Follow-up				X	X	X	X	X	X	X	X	X	X	X	X
Data Entry/Cleaning				X	X	X	X	X	X	X	X	X	X	X	X
Analysis/Report Writing													X	X	X

several experts (see Section 2.14 for letters of support): [name] (safety of smoking cessation medications in pregnancy), [name] (sex hormones and addiction), [name] (obstetrician), and [name] (neuropsychological nicotine response).

Study Timeline. The timeline is displayed in **Table 4**.

Future Directions. The expected outcomes of this project will be a better understanding of the relationship between sex hormones and smoking-related symptomatology. Upon completing this project, we intend to continue our exploration into the role of sex hormones on smoking behavior. Specifically, if our expectations are confirmed, we will conduct additional studies to investigate the possibility of exogenous progesterone as a treatment for smoking cessation and relapse prevention in several different populations including pregnant women, during the postpartum period and non-pregnant women.

INCLUSION OF WOMEN AND MINORITIES

This study will only be recruiting women because the research question addressed is only relevant to one sex. We are looking specifically at the effects of female sex hormones on smoking behavior and nicotine response in pregnant and oral contraceptive users. The study will use participants recruited from the greater metropolitan area of Minneapolis and St. Paul, via two clinical sites and mass media advertisements. The Twin Cities metropolitan area has a sufficiently large female smoking population to ensure an adequate sample. We have been successful in recruiting similar numbers of women in similar periods of time in previous studies. Estimates indicate that as of 2009 the Minneapolis and St. Paul, Minnesota Twin Cities metro area included approximately 50.5% female and 20.2% of the population in the racial minority groups (Black= 11.0%, Asian = 5.8%, American Indian = 1.2%, other = 4.0%) and the Hispanic population is 6.4%. If minority women do not respond to the advertisements, we will make special efforts to solicit their participation by advertising in local neighborhood newspapers with high minority readership (such as the Southside Pride, Phillips/Powderhorn, and Riverside Editions); by posting flyers in free clinics in the metro area who service minorities (e.g., Community University Healthcare Center, Pilot City); and by identifying contacts in churches, health centers, and community centers with high minority participation and disseminating information regarding the study opportunity; and once we have garnered initial contact with participants we receive multiples word of mouth referrals. Our current study has been successful in recruiting a diverse sample in that of the 212 participants enrolled to date 48% are White, 29% are Black, 9% are more than one race and 14% are other.

INCLUSION OF CHILDREN

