
RESEARCH PLAN

Overview. Using two clinical models – pregnancy (Sample 1) and oral contraceptives (OC; Sample 2) – we aim to (1) examine the association between levels of progesterone (Prog), allopregnanolone (Allo) and the estradiol/progesterone (E2/P) ratios with smoking-related symptomatology during ad libitum smoking, and (2) determine the association between Prog, Allo, and E2/P with the changes in smoking-related symptomatology and response to nicotine following overnight abstinence. Sample 1 will enroll approximately 112 pregnant women to ensure a final sample size of 84 participants to participate in a cross-sectional study at two time points: 12 weeks to 22 weeks gestation (n=42) and 32 to 37 weeks gestation (n=42). Sample 2 will enroll approximately 78 OC users to ensure a final sample size of 52 participants in a randomized cross-over, double-blind study design to complete testing periods during “low” and “high” dose levels of exogenous progesterone with a consistent dose of exogenous estrogen. All participants will complete identical data collection procedures including providing saliva (cortisol to measure stress), urine (cotinine and 3-Hydroxycotinine to measure nicotine exposure, and medication compliance), and blood (progesterone, allopregnanolone, estradiol, and nicotine) samples, as well as ecological momentary assessments (EMA) daily for seven-days. Participants will also complete a three-hour smoking lab session (with the first morning

cigarette) and a four and a half-hour nicotine exposure lab session (after at least 13 hours of overnight abstinence). These sessions will contain a nicotine challenge via nicotine nasal spray or smoking topography with timed-series of physiological, subjective and behavioral responses.

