- (9) Salivary Cortisol (Day 5 only): Five saliva samples over the course of the day given that cortisol, a physiological measure of stress released by the hypothalamic-pituitary adrenal axis (HPAA), has a clear diurnal variation. Its peak activity occurs about 8:00 am in the normal sleeper, followed by steady decline until noon. The lowest activity occurs around 8:00 pm. The frequent sampling in the morning will be used to assess free cortisol responses to awakening. Awakening cortisol increase is considered a promising marker of adrenocortical functional status.⁵⁵⁻⁵⁷

For Aim 2, the outcomes will be assessed following overnight abstinence: (1) the change in smoking-related symptomatology (items 1-6 above), and (2) response to nicotine (described below). We have a nearly identical timed series to assess nicotine response with success in our ongoing study. All items will be self-administered per direction of study staff via a computer program (REDCap; <http://project-redcap.org/>) to improve the quality of data (by avoid missing data, illegible data, etc) and limit amount of time spent on data entry and cleaning. The following seven *dependent measures* were selected to assess seven domains of nicotine response:⁴¹

- (1) Physiological Measures: Blood pressure (BP) and heart rate (HR) will be measured using a Dinamap S X/P. This device is an automated device that will read BP and HR simultaneously by placing a blood pressures cuff above the antecubital fossa region of the arm.
- (2) Subjective Response: The Subjective State Scale (SSS) questionnaire is comprised of 24-items to assess positive affect, distress and nicotine withdrawal symptoms.⁵³⁻⁵⁴ Participants will rank each item based on how they felt over the past 5-30 minutes (depending on time of last completion) using a seven-point scale ranging from 'not at all' to 'very strong.' This form takes approximately two minutes.
- (3) Motor Speed: During the Finger Tapping (FT) task,⁵⁸ participants are instructed to use the index finger on the dominant hand to tap a key on a computer as quickly as possible for 30 seconds. This task takes about 1.5 minutes.

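### Aim 2 defines its symptom outcome as a change with overnight abstinence, but Hypothesis 2a analyses only the post-abstinence level

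*Combined protocol and SAP*

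**What the plan says.** The Research Plan overview gives the second aim as relating the hormones "with the changes in smoking-related symptomatology and response to nicotine following overnight abstinence". Under Study Measures, the first Aim 2 outcome is "the change in smoking-related symptomatology (items 1-6 above"). Table 3 assigns both kinds of rating to Aim 2: symptoms during ad libitum "smoking (Day 0, Day 7) and after overnight abstinence (Day 8").

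The Statistical Analysis section does something else. For Sample 1, Hypothesis 2a reads "we will investigate the association between Prog and self-reported craving after overnight abstinence with a linear regression model", followed by a multiple regression "with consideration of other baseline measures, such as cigarettes/day and FTND score". For Sample 2, "we will use self-reported craving, urges to smoke and stress collected after overnight abstinence", compared between dose levels with the terms given for Hypothesis 1 (dose, period, sequence, random intercept). Neither text subtracts an ad libitum rating or names one as a covariate. By contrast, the nicotine-exposure outcomes are explicitly defined as post-spray values minus baseline.

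The only craving-change analysis is under Hypothesis 1 in Sample 1: "comparing the change in Prog with the change in self-reported craving from Day 0 to Day 7".

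**The concern.** The analysis does not estimate the quantity the aim names. Post-abstinence craving equals ad libitum craving plus the change. If progesterone is related to ad libitum craving, which is what Hypothesis 1 proposes, that relation appears in the post-abstinence level even when progesterone has no bearing on how craving responds to abstinence. A positive 2a result could then be reported as an effect on the abstinence response.

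The reference for a change is also unsettled. Table 3 treats Day 7 as ad libitum. The procedures tell women at the Day 6 visit to stop smoking by midnight, and say that the symptom ratings before the Day 7 smoking lab session follow overnight abstinence. An analyst working from Table 3 could subtract Day 7 from Day 8 and compare two abstinent ratings. Day 8 itself is not in dispute: the overview places the nicotine session "after at least 13 hours of overnight abstinence", and Table 3 agrees.

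**Working it through.** **Inputs.** From Sample Size & Power Analysis: n=84, r=0.30, 81% power; n=52, d=0.40, 80% power; two-sided 0.05. Not in the documents and therefore assumed: the ratio k of post-abstinence to ad libitum SD, and the correlation c. In Sample 1, c is between the two ratings. In Sample 2, k and c refer to the within-woman high-minus-low differences in those ratings.

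**1. The plan's own figures.** Sample 1: noncentrality r/√(1−r²)·√n = 0.3145 × 9.165 = 2.88, power 81.3%. Sample 2: d√n = 0.40 × 7.211 = 2.88, power 80.8%. Both reproduce, so the issue is the outcome, not the arithmetic.

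**2. Effect on ad libitum craving only, none on the change.** Write A for the ad libitum rating (SD 1) and B for the post-abstinence rating (SD k).

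Sample 1: cov(Prog, A) = cov(Prog, B) = 0.30, so corr(Prog, B) = 0.30/k and cov(Prog, B−A) = 0. Sample 2: the dose contrast is 0.40 in both ratings, so the standardised contrast for B is 0.40/k.

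| k | Sample 1: r for B | Level significant | Sample 2: d for B | Level significant |
|---|---|---|---|---|
| 1 | 0.30 | 81% (simulated 80%) | 0.40 | 81% |
| 1.25 | 0.24 | 61% (60%) | 0.32 | 62% |
| 1.5 | 0.20 | 46% (45%) | 0.27 | 47% |
| 2 | 0.15 | 28% | 0.20 | 29% |

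In simulations at k = 1 to 1.5 (40,000 replicates), the change score rejects in 4.8% to 5.1% of trials in Sample 1 and 4.8% to 5.2% in Sample 2 (Day 8 minus on-dose Day 6). The level percentages are not type I error rates: the level association is real in this scenario. They show how often there would be a significant result open to misreading.

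**3. The reference visit in Sample 2.** The first capsule is taken at 7PM after the Day 0 visit. Without carry-over, the Day 0 dose contrast is 0, and the contrast in Day 8 minus Day 0 is 0.40 − 0 = 0.40, the same as for the level. At k=1 its standardised size is 0.40/√(2−2c) = 0.338, 0.365, 0.400 or 0.447 at c = 0.3, 0.4, 0.5 or 0.6, and it is significant in 67%, 73%, 81% or 89% of trials. Subtracting Day 0 therefore does not isolate the abstinence response. Against on-dose Day 6 the contrast is 0.40 − 0.40 = 0.

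**4. Power cost of the change.** Take the opposite case: an effect confined to the abstinence response, sized to give the level 81% power at each k. The change has SD √(1+k²−2ck), so its effect is 0.30k/√(1+k²−2ck) in Sample 1, with 0.40 in place of 0.30 in Sample 2.

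| k | c | Sample 1 power | Sample 2 power |
|---|---|---|---|
| 1 | 0.3 | 66% | 67% |
| 1 | 0.4 | 73% | 73% |
| 1 | 0.5 | 81% | 81% |
| 1 | 0.6 | 90% | 89% |
| 1.25 | 0.3 | 75% | 75% |
| 1.25 | 0.4 | 81% | 81% |

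The change is noisier than the level when 1+k²−2ck > k², that is when c < 1/(2k): below 0.50, 0.40 or 0.33 at k = 1, 1.25 or 1.5. At k=1 and c=0.3 the multiplier is √1.4 = 1.183, so the detectable effects rise from 0.30 and 0.40 to about 0.35 and 0.47.

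**The case against.** - **Loose wording.** The formal specific aims are not in the supplied text, and the Statistical Analysis section speaks of average symptom levels while reserving changes for the nicotine outcomes. This possibility stands. But that sentence draws on Day 0 and the EMA week, so it describes the ad libitum outcome. Change is stated in two separate places, and Table 3 collects both ratings for Aim 2. The sections disagree whichever was meant.
- **Sample 2 is less exposed.** This stands. The dose comparison of the level is a valid randomised contrast, and the problem appears only against an on-dose ad libitum reference. Table 3 does not list Day 6 for Aim 2.
- **Circular magnitudes.** The scenario assumes a real association with the level and reports the power to find it. That is true, and the figures should be read only as illustration. They fall to 28% and 29% at an SD ratio of 2.
- **Covariate adjustment instead.** The Sample 1 covariate wording permits adjusting for ad libitum craving but does not require it. For the effect in step 4, with equal SDs, adjustment has more power in Sample 1: about 83% to 84% at correlation 0.3 and 90% to 91% at 0.5. It answers a conditional question, though. With no effect on the change, SD ratio 1 and correlation 0.5, it still rejects in about 38% of trials, so it does not target the stated change.
- **Hypothesis 1 would reveal an ad libitum association.** It would, but comparing two separate tests does not estimate the change.

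**Conclusion.** The concern holds. As written, Hypothesis 2a does not deliver the Aim 2 symptom outcome in either sample, and a significant 2a result cannot by itself be read as a response to abstinence. The Hypothesis 1 change analysis does not repair this: it relates change in craving to change in progesterone, from Day 0 to Day 7, in Sample 1 only.

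With SD ratios of 1 to 1.5, an ad libitum effect of the plan's own detectable size and no effect on the change, the level would be significant in roughly 45% to 80% of trials, against about 5% for the change from an on-dose reference. These figures rest on assumed SD ratios and an assumed ad libitum effect. The textual mismatch rests on neither. This should be corrected, but it does not invalidate the level as an outcome. Confidence is medium, because the formal aims cannot be read.

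**What to change.** Define the 2a outcome as post-abstinence craving minus the ad libitum clinic rating on the same form in the same testing period. Keep the planned models, treat the secondary symptom outcomes the same way, and report the level alongside.

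Name the reference visit in advance. Day 6 fits: it is on-dose in Sample 2, precedes the midnight quit instruction and uses the same forms (Table 2). State its limits: women are asked not to smoke for one hour beforehand, and no clock time is given, whereas Day 8 starts between 7 and 10 am. Use the pre-quit EMA mean only as a sensitivity analysis, since its prompts fall at random between 7 am and 11 pm and Table 3 assigns EMA to Aim 1. Reconcile Table 3 with the smoking lab session text on Day 7, and name the single visit that supplies the post-abstinence value.

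Alternatively, restate Aim 2 as a post-abstinence level and do not interpret 2a as a change in response to abstinence.

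The cost is SAP wording and one subtraction of data already collected, with no new visits. The change loses power when the correlation is below 1/(2 × SD ratio), so the stated 81% and 80% should not be carried over to it.

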At the *follow-up clinic visit (Day 6)*, participants will return to the clinic. Upon arrival, participants will have their weight measured and provide urine (nicotine exposure and medication compliance via visual inspection of urine color which will change due to riboflavin medication filler) and blood (sex hormones) samples. Remaining blood and urine will be saved in the biorepository. Next, participants will complete self-reported items of smoking-related symptomatology and related factors (See Table 2 and Section E.5 for details) followed by measurement of blood pressure and heart rate. While participants are completing the questionnaires study staff may complete a NicAlert (Appendix C) to confirm self-reported smoking status (NicAlert level of ≥ 3 indicating a cotinine value of ≥ 100 ng/mL). Participants will then practice using the nicotine nasal spray but will be prompted to refrain from smoking for one hour prior to the visit to limit nicotine exposure. They will also practice smoking through the smoking topography machine and practice using the computer tasks and other measures used in the lab sessions (See Section E.5. for details). Finally, participants will be instructed to quit smoking by midnight (Appendix D). Upon the completion of this visit, the lab session will be confirmed and participants will be compensated for their time.

Figure 6. Nicotine Lab Sessions

The *smoking lab session*

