will occur on *Day 7*. At this visit, participants will smoke their first morning cigarette (i.e. they will be instructed to not smoke on Day 7 until instructed to do so by study staff). Participants will attend a three hour visit beginning as close to their usual first morning cigarette as possible (starting at approximately 7am-10am, per participant preference). Puff topography, a precise measure of smoking behavior,^{67,68,69} will be used to examine whether prolonged use of progesterone affects topography measures that may indicate smoking compensation.⁷⁰ Puff topography will be assessed using a handheld topography device (type pending) that provides a valid measurement of puff number, puff volume, inter-puff interval and other indices.⁶⁶ Carbon monoxide readings will be collected before and 2-5minutes after puff topography.³⁶ Prior to the initiation of the lab session, participants will have their weight, blood pressure, and heart rate measured, and they will complete subjective measures to assess their self-reported level of smoking-related symptomatology and related factors after overnight abstinence (See Table 2 and Section E.3.5 for details). Once the smoking lab session begins, participants will be instructed to turn off their cell phones and will not be allowed to consume caffeinated beverages or any food items. Measurements of smoking response will start 40 minutes prior to the participant smokes her cigarette and will be administered in a fixed order (**Figure 6**). Response to smoking will be quantified via seven performance domains known to be associated with nicotine response:⁴¹ (1) physiological (blood pressure, heart rate), (2) subjective (Subjective State Scale); (3) motor speed (Finger Tapping) (4) episodic memory (Word Recall); (5) working memory (2-Back); (6) attention/impulsivity (Immediate Memory Task), and (7) delayed memory (Delayed Memory Task). (See Section E.5. for more details.) In order to access plasma nicotine levels, a blood draw via an intravenous catheter will occur at baseline (-1 minute before smoking a cigarette) and +2 minutes after the last puff of the cigarette. A total of 30cc of blood will be collected. 15 cc of blood will be analyzed for nicotine levels and hormone levels and 15 cc of blood will be added to the biorepository.

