The *nicotine exposure lab session* will occur on *Day 8*. Participants will attend this four and a half-hour visit in the morning (beginning at 7am-10am depending on participant preference) to control for diurnal variation in outcome variables. While participants are completing the questionnaires study staff will download the information from the EDCs. Procedures will be identical to Day 7 except instead of subject smoking a cigarette, they will administer nicotine nasal spray and repeat the protocol twice. Nicotine nasal spray (Nicotrol, Pharmacia & Upjohn; Appendix A) is an FDA-approved use of nicotine delivery. One spray delivers 0.5 mg of nicotine; therefore, one dose (four sprays - two in each nostril) is approximately equivalent to the

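### The analysis section treats Day 7 as an ad libitum symptom day and one of two hormone days; the visit procedures contradict the first and leave the second unsettled

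*Combined protocol and SAP*

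**What the plan says.** Three statements in Statistical Analysis rest on Day 7.

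- Table 3, Aim 2 line: symptoms are collected during ad libitum "smoking (Day 0, Day 7) and after overnight abstinence (Day 8"). Day 7 is grouped with Day 0, and only Day 8 counts as abstinent.
- Sample 1, Hypothesis 1: after the regression on levels, there is a further analysis "comparing the change in Prog with the change in self-reported craving from Day 0 to Day 7".
- Hormone predictor: the text averages the Day 0 and Day 7 values, and Table 3 lists "Serum progesterone, allopregnanolone, and estradiol (Day 0, Day 7").

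The procedures and measures sections describe the days differently.

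- Day 6 visit: "participants will be instructed to quit smoking by midnight".
- Day 7 smoking lab session, before the cigarette: "they will complete subjective measures to assess their self-reported level of smoking-related symptomatology and related factors after overnight abstinence".
- Study Measures defines the Aim 1 outcome as symptom level during ad libitum smoking, and the Aim 2 symptom outcome as a change assessed following overnight abstinence.
- Table 2 and Study Measures put the hormone draws on Days 0, 6 and 8. Study Measures gives averaging as the reason for taking three.
- The Day 7 smoking lab text also sends blood for hormone assay, although Table 2 leaves that cell empty.

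**The concern.** An analyst works from the analysis section. Followed literally, it puts a rating made after a night without smoking into a change score meant to describe ad libitum smoking. It also builds the hormone predictor from a day that the sampling schedule does not list, leaving out two days that it does.

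For symptoms, the stake is what the Sample 1 change analysis means. Hypothesis 1 concerns ad libitum smoking and Hypothesis 2a concerns the abstinent state; a Day 7 clinic rating blurs the two. Aim 2 carries a similar risk. If its symptom change were computed from Table 3's ad libitum days, one abstinent morning (Day 7) would sit in the reference for another (Day 8).

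For hormones, the stake is the definition and scale of the stated independent variable. In Sample 2 the choice of days decides how much weight a pre-dose value receives.

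**Working it through.** **The plan's own figure.** Inputs from Sample Size & Power Analysis: n = 84, r = 0.30, two-sided 0.05. Noncentrality = r/√(1 − r²) × √n = 0.30/√0.91 × √84 = 2.88 on 82 df, which gives power 81.3%, against 81% stated. This is power for the regression of craving level on Prog. It does not depend on the Day 7 change score.

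**Symptom state on each clinic day, if instructions are kept.**

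| Day | Procedures | Table 3, Aim 2 |
|---|---|---|
| 6 | ad libitum, with a requested pause of one hour | not listed |
| 7 | no smoking from midnight to a 7–10am start: at least 7–10 h | ad libitum |
| 8 | abstinent, at least 13 h according to the Overview | abstinent |

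The last clinic rating before the quit instruction takes effect is therefore Day 6.

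**Effect on the change score.** Write the Day 7 clinic rating as C7 = C7(ad libitum) + A, where A is a woman's overnight shift. The analysed change is [C7(ad libitum) − C0] + A, regressed on the change in Prog.

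- If A is equal in all women, only the intercept moves.
- If A varies but is unrelated to the change in Prog, residual noise rises.
- If A is related to the change in Prog, the slope gains Cov(A, ΔProg)/Var(ΔProg), and Hypotheses 1 and 2a are mixed.

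The documents give no value for A, so no numerical bias or loss of power can be derived.

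**Hormone days.** Days 0 and 7: Statistical Analysis text and Table 3. Days 0, 6 and 8: Table 2 and Study Measures. Day 7 assay: smoking lab text only. The Day 8 session text names progesterone and allopregnanolone but not estradiol, whereas Table 2 lists the E2/P ratio for Day 8. For nicotine, Table 2 and the plasma nicotine item list Day 8 only, while the smoking lab text also draws nicotine blood on Day 7.

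**Scale of the Sample 2 predictor.** Under Sample 2 - Timing of Testing Period, the first capsule is taken at 7PM after the Baseline Visit, so the Day 0 draw is pre-dose. Assume a common Day 0 level B, and on-dose levels L (low) and H (high).

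- Days 0 and 7: (B + H)/2 − (B + L)/2 = (H − L)/2, or 1/2 of the on-dose contrast.
- Days 0, 6 and 8, if dosing covers Day 8: (B + 2H)/3 − (B + 2L)/3 = 2(H − L)/3, or 2/3.

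The same fractions hold for Allo, and for E2/P if daily ratios are averaged. Sample 1 has no pre-dose draw. The choice of days therefore rescales the dose-driven part of the predictor in one sample only, and this enters the group-by-Prog interaction in the comparison of the two samples.

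**The case against.** **The labels look like leftovers.** Table 3 has "Nicotine response measures collected during three-hour lab session (Day 8"), whereas the procedures say of Day 8 "Participants will attend this four and a half-hour visit in the morning". That suggests a table not updated when visits were renumbered. It explains the conflict, but the outdated labels are in the section that governs the analysis.

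**The symptom reach is narrow.** This stands. As written, Hypotheses 2a and 2b name no Day 7 symptom reference, and the Sample 2 primary tests do not use the Day 0 to Day 7 change. What remains is one additional Sample 1 analysis, and the plan does not say whether its Day 7 craving is the clinic form or the EMA. The EMA would avoid the pre-cigarette rating, but whether smoking is allowed for the rest of Day 7 is itself unsettled.

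**Neither day is clean.** Day 7 is timed to the usual first cigarette, so the gap is roughly a normal night. On Day 6 women "will be prompted to refrain from smoking for one hour prior to the visit". Both points are fair, but the protocol itself calls the Day 7 state abstinent and gives Day 6 no such label.

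**A reader might infer that no Day 7 hormone value will exist, or that most draws are discarded.** The documents do not support this. The smoking lab text has Day 7 blood assayed for hormones, and any count of lost draws assumes that Table 2 overrides it. What can be said is that the sections disagree and that the stated average omits Days 6 and 8.

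**Conclusion.** The inconsistency is real and should be fixed; its consequence is modest. Table 3's ad libitum label for Day 7 contradicts the procedures for the clinic forms. The Sample 1 Hypothesis 1 change analysis is compromised if those forms supply Day 7 craving. The hormone predictor conflicts with the sampling schedule, and the documents disagree on whether Day 7 is a hormone day at all.

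In Sample 2 the averaged predictor carries 1/2 of the on-dose contrast with Days 0 and 7, against 2/3 with Days 0, 6 and 8. This assumes that Day 0 levels do not differ by dose and, for the second figure, that dosing covers the Day 8 draw. It bears on the Sample 2 Allo and E2/P analyses and on the between-sample interaction.

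A reader might go further and infer that the primary results or the power are undermined. They are not shown to be: the Sample 2 primary tests use dose level as the factor, and the 81% does not depend on these day labels. No consequence has been quantified for the Sample 1 hormone average.

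**What to change.** In the Statistical Analysis text and Table 3:

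1. Name Day 6 as the last ad libitum clinic rating. Analyse the Sample 1 Hypothesis 1 change in craving and Prog from Day 0 to Day 6, and say that the clinic rating is used.
2. Class the Day 7 pre-cigarette ratings as abstinent, and do not use them as an ad libitum reference for any Aim 2 change.
3. Reconcile Table 2, Study Measures, both lab session descriptions, the plasma nicotine item, the Statistical Analysis text and Table 3 on which days' blood is assayed for hormones and for nicotine, including whether estradiol is assayed on Day 8.
4. Then define the hormone average on the reconciled draws (Days 0, 6 and 8 under Table 2 and Study Measures), and state how the pre-dose Day 0 draw enters in Sample 2.
5. State the second clinic day in the averaged symptom outcome. The text as read shows Day 0 and then a day without a number, which may be an extraction fault.

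Separately, two sets of statements must be reconciled by the sponsor. The first is the Day 6 midnight quit, the Day 7 cigarette and the minimum of 13 hours before Day 8: midnight to a 7–10am start is only 7–10 hours, and 13 hours before a 7–10am Day 8 start falls at 6–9pm on Day 7. The second is the seven days of capsules and the Day 8 draw: 14 twice-daily doses counted from 7PM on Day 0 end at 7AM on Day 7, yet the testing period is called eight days, further medication may be supplied at visits, and compliance is checked on Day 8.

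The analysis changes cost wording only, because Day 6 symptoms and hormones are already collected. The drawbacks are the requested one-hour smoking pause before the Day 6 visit and a change interval of 6 days instead of 7.
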